5.2 Exclusion Criteria

Volunteers will be excluded from study participation for any of the following:

1. History or presence of clinically significant cardiovascular (heart murmur), pulmonary, hepatic, renal, hematologic, gastrointestinal, endocrine, immunologic, dermatologic, neurologic, psychiatric disease, or any other condition that, in the

- opinion of the Investigator, would jeopardize the safety of the subject or the validity of the study results.
- 2. Any presence of musculoskeletal toxicity (severe tenderness with marked impairment of activity, or frank necrosis).
- 3. Surgery within the past 90 days prior to dosing as determined by the Investigator to be clinically relevant.
- 4. History or presence of alcoholism or drug abuse within the past 2 years as determined by the Investigator to be clinically relevant.
- 5. Participation in another clinical trial within 30 days prior to dosing.
- 6. Female subjects who are pregnant or lactating.
- 7. Positive result on a urine drug/alcohol screen at screening or check-in.
- 8. Positive result on urine cotinine at screening.
- 9. Has the following laboratory abnormalities at screening:
 - a. ALT or AST Grade 2 or greater (≥ 2.0 times ULN)
 - b. Creatinine Grade 2 or greater (≥1.6 times ULN)
 - c. Pancreatic lipase Grade 2 or greater (≥1.6 times ULN)
 - d. Amylase Grade 2 or greater (≥1.6 times ULN)
 - e. Total bilirubin Grade 2 or greater
 - f. CPK (> 1.25 times ULN)

If exclusionary lab criteria are met, values may be confirmed by repeat evaluation.

- 10. Has a positive test for hepatitis B surface antigen, hepatitis C antibody, or HIV at screening.
- 11. Seated blood pressure (BP) is less than 90/40 mmHg or greater than 140/90 mmHg at screening, Day -1 (check-in) or predose. Out-of-range vital signs may be repeated once for confirmation. Out of range values will not be considered AEs if the repeat assessment is in range.
- 12. Seated heart rate is lower than 40 beat per minute (bpm) or higher than 99 bpm at screening, Day -1 (check-in) or predose. Out-of-range vital signs may be repeated once for confirmation. Out of range values will not be considered AEs if the repeat assessment is in range.
- 13. Any clinically significant ECG abnormality at screening (as deemed by decision of the Investigator and the Sponsor's Medical Monitor).

NOTE: The following may be considered not clinically significant without consulting the Sponsor's Medical Monitor:

- Mild first degree A-V block (P-R interval <0.23 sec)
- Right or left axis deviation
- Incomplete right bundle branch block
- Isolated left anterior fascicular block (left anterior hemiblock) in younger athletic subjects
- 14. QTcF interval >450 msec for males or >470 msec for females at screening, Day -1, or Day 1 (predose), or history of prolonged QT syndrome. For the triplicate ECGs taken at screening and on Day -1, the average QTcF interval of the 3 ECG recordings will be used to determine qualification.
- 15. Family history of long-QT syndrome or sudden death without a preceding diagnosis of a condition that could be causative of sudden death (such as known coronary artery disease, congestive heart failure, or terminal cancer).
- 16. Use of any prescription medication within 14 days prior to dosing.
- 17. Use of any over-the-counter (OTC) medication, including herbal products and vitamins, within 7 days prior to dosing, except acetaminophen. Up to 3 grams per day of acetaminophen is allowed only at occasional use and at the discretion of the Investigator prior to dosing.
- 18. Use of any drugs or substances known to be significant inhibitors of cytochrome P450 (CYP) enzymes and/or significant inhibitors or substrates of P-glycoprotein (P-gp) and/or organic anion transporting polypeptides (OATP) within 14 days prior to the first dose of study drug.
- 19. Use of any drugs or substances known to be inducers of CYP enzymes and/or P-gp, including St. John's Wort, within 30 days prior to the first dose of study drug.
- 20. Blood donation or significant blood loss within 56 days before the first dose of study medication until the end-of-study visit.
- 21. Plasma donation within 7 days before the first dose of study medication until the end-of-study visit.
- 22. Has been on a significantly abnormal diet during the 4 weeks preceding the first dose of study medication.
- 23. Unwilling to remove any artificial nails (e.g. acrylic, gel) or fingernail polish and not use such products for the duration of the study.

- 24. History or presence of allergic or adverse response to Listerine breath strips or aspartame.
- 25. Is lactose intolerant.

5.3 Medication and Activity Restrictions

- 1. Subjects must not donate blood from 56 days or plasma from 7 days prior to the first dose of study medication until the last follow-up visit or early withdrawal visit is completed. It is recommended that blood/plasma donations not be made for at least 30 days after the last follow-up visit or early withdrawal visit.
- 2. Subjects must not use tobacco- or nicotine-containing products (including smoking cessation products) from 6 months prior to the first dose of study medication until the last follow-up visit or early withdrawal visit is completed.
- 3. Subjects must not consume alcohol from 72 hours prior to the first dose of study medication until the last follow-up visit or early withdrawal visit is completed. However, allowance for an isolated single incidental consumption may be evaluated and approved by the study Investigator based on the potential for interaction with the study drug.
- 4. Subjects must not consume beverages or foods that contain grapefruit or Mandarin oranges from 10 days before the first dose of study medication, or poppy seeds, broccoli, Brussels sprouts, pomegranate, star fruit, char-grilled meat, or caffeine/xanthine from 24 hours before the first dose of study medication, until the last follow-up visit or early withdrawal visit is completed. Subjects will be instructed not to consume any of the above products; however, allowance for an isolated single incidental consumption may be evaluated and approved by the study Investigator based on the potential for interaction with the study drug.
- 5. Subjects must not engage in strenuous exercise from 48 hours prior to the first dose of study medication until after discharge from the clinic. For follow-up visits, subjects must not engage in strenuous exercise during the 3 days prior to the visit. Any report of exercise will be documented and recoded as a protocol deviation. Subjects may continue in the study at the discretion of the study Investigator.
- 6. Subjects must be willing to remove any artificial nails (e.g., acrylic, gel) or fingernail polish and not use such products for the duration of the study.

5.4 Screening

The informed consent documents (ICDs) will be discussed with each potential participant, and each individual will sign an ICD for the study before any study-specific procedures being performed.

Each potential study participant will have the following assessments by the Investigator or designee within 28 days (21 days for Part 3) before study start:

- Demographic data, including sex, age, race, ethnicity, body weight (kg), height (cm), BMI (kg/m²), and smoking habits.
- Medical history
- Physical examination
- Vital signs (blood pressure, pulse rate, respiration rate, temperature, and pulse oximetry)
- Triplicate 12-lead safety ECGs
- Clinical laboratory tests (hematology, coagulation, chemistry, and urinalysis)
- Serology tests for HIV, hepatitis B and C
- Urine test for drugs of abuse and cotinine
- Serum pregnancy (all female subjects)
- FSH test (Post-menopausal females)
- Concomitant medication review

Only medically healthy subjects with clinically acceptable laboratory profiles and ECGs within the defined parameters who fulfill all other inclusion criteria and meet none of the exclusion criteria outlined in the previous sections will be enrolled in the study.

Subjects will be assigned numbers in an ascending order, based on successful completion of the screening process.

6 STUDY PROCEDURES

6.1 Subject Assignment

For Part 1, 6 dose levels are planned. For 6 dose levels, 6 cohorts of 8 subjects will be used, 6 to receive active drug and 2 to receive placebo, all under fasting conditions.

In addition, the effect of food on bioavailability of TBAJ-876 will be studied in a food-effect cohort comprised of two parallel groups, one fasting and the other fed. The fed group will enroll at least 10 subjects, which will yield complete data for at least 8 subjects if at most 2 fail to complete. For the fasted group, the data from the 6 subjects previously administered 100 mg TBAJ-876 in Cohort 4 (who have already completed the cohort) will be combined with data from 3 additional subjects to be enrolled in this fasted group. This will yield a complete data set for at least 8 subjects if at most 1 fails to complete. Thus, the total number of subjects planned is at least 50 to 60.

Food-Effect: Based on exposure levels from the first 4 completed cohorts, the 100 mg dose was chosen for the food-effect cohort. Therefore, all subjects in the food-effect cohort will receive active drug of TBAJ-876, 100 mg. In this food-effect cohort, new subjects will be enrolled in two parallel groups, one fasting and the other fed. The fed group will enroll at least 10 subjects and the fasted group will include data from 6 subjects who completed Cohort 4 and 3 additional subjects to be enrolled in the fasted group.

Additional cohorts (8 subjects per cohort) may be enrolled if it is deemed appropriate by the Sponsor to repeat a dose level, to study another dose level, or to increase cohort size (subject numbers).

Additional cohort, Cohort 7: Eight (8) subjects will be enrolled, 6 to receive active drug and 2 to receive placebo. Subjects will receive a single dose under fasted conditions. Subjects will receive 800 mg TBAJ-876 or matching dose of placebo for TBAJ-876 Oral Suspension.

For Part 2, 39 subjects are planned to be enrolled. There are 3 cohorts planned. Cohort 1 with 12 subjects per cohort (9 to receive active drug and 3 to receive placebo), Cohort 2 with 13 subjects per cohort (9 to receive active drug and 4 to receive placebo), and Cohort 3 with 14 subjects per cohort (9 to receive active drug and 5 to receive placebo). All doses in Part 2 will be under fed conditions.

The number of subjects selected for the study was based on the adequate number considered to provide sufficient safety data. This study has not been formally powered.

Each subject will receive an assigned treatment (active or placebo) based on the randomization schedule prepared by the unblinded statistician. The unblinded pharmacy staff will ensure compliance with the randomization schedule.

For Part 3, 30 subjects are planned to be enrolled. There are 3 groups planned with 10 subjects per group. All subjects will receive active drug under fasted or fed conditions.

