Part 1:

Plan to enroll 50 to 60 subjects in 6 SAD cohorts. Each cohort will consist of 8 subjects, 6 to receive active drug and 2 to receive placebo, all under fasting conditions.

In addition, the effect of food on bioavailability of TBAJ-876 will be studied in a food-effect cohort comprised of two parallel groups, one fasting and the other fed. The fed group will enroll at least 10 new subjects, which will yield complete data for at least 8 subjects if at most 2 fail to complete. Six subjects previously administered 100 mg TBAJ-876 in Cohort 4 (who have already completed the cohort) will be considered part of the fasted group. At least three additional subjects will be enrolled to be dosed in the fasted group. This will yield a complete data set for at least 8 subjects if 1 fails to complete. Based on exposure levels from the first 4 completed cohorts, the 100 mg dose was chosen for the food-effect cohort. Therefore, all subjects in the food-effect cohort will receive active drug of TBAJ-876, 100 mg.

Additional cohort, Cohort 7: Eight (8) subjects will be enrolled, 6 to receive active drug and 2 to receive placebo. Subjects will receive a single dose under fasted conditions. Subjects will receive 800 mg TBAJ-876 or matching dose of placebo for TBAJ-876 oral suspension.

Part 2:

Planned to enroll 39 subjects in 3 MAD cohorts. Cohort 1 with 12 subjects per cohort (9 to receive active drug and 3 to receive placebo), Cohort 2 with 13 subjects per cohort (9 to receive active drug and 4 to receive placebo), and Cohort 3 with 14 subjects per cohort (9 to receive active drug and 5 to receive placebo. All cohorts will receive the assigned dose under fed conditions.

Additional cohorts may be enrolled if deemed appropriate by the Sponsor to repeat a dose level or to study another dose level or to increase number of subjects based on PK and safety information learned from initial cohorts. These decisions on additional cohorts will not take place until the Sponsor, in conjunction with the Principal Investigator, has determined that adequate safety, tolerability, and pharmacokinetics from the previous cohorts have been demonstrated. The Institutional Review Board (IRB) should be immediately notified of this revised approach.

Part 3:

Planned to enroll 30 subjects in 3 groups of 10 subjects each. All groups to receive active drug under fasted or fed conditions.

- Group 1: Single dose 1 x 100 mg tablet fasted
- Group 2: Single dose 1 x 100 mg tablet fed

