## 4 SAMPLE SIZE

For Part 1, 7 dose levels are planned. For 7 dose levels, 7 cohorts of 8 subjects will be used, 6 to receive active drug and 2 to receive placebo, all under fasting conditions.

QMD Ref: Worldwide-TMP-ST-006-4.0 Effective: 12Aug2019	Governing QMD: Worldwide-SOP-ST-001
Confidentiality Statement	

This document is the property of Worldwide Clinical Trials Inc. and may not be duplicated, copied, altered or removed from company without prior approval from Worldwide Quality Assurance or in compliance with Worldwide Standard Operating Procedures.

Worldwide Clinical Trials Controlled Quality Management Document		
 WORLDWIDE CLINICAL TRIALS	Sponsor:	Global Alliance for TB Drug Development
	Protocol Number:	TBAJ-876-CL001
STATISTICAL ANALYSIS PLAN – PHASE 1		

The effect of food on bioavailability of TBAJ-876 will be studied in a food-effect cohort comprised of two parallel groups, one fasting and the other fed. The fed group will enroll at least 10 subjects, which will yield complete data for at least 8 subjects if at most 2 fail to complete. For the fasted group, the data from the 6 subjects previously administered 100 mg TBAJ-876 in Cohort 4 (who have already completed the cohort) will be combined with data from 3 additional subjects to be enrolled in this fasted group. This will yield a complete data set for at least 8 subjects if at most 1 fails to complete. Thus, the total number of subjects planned is at least 60 to 70.

For Part 2, 39 subjects are planned to be enrolled. There are 3 cohorts planned. Cohort 1 with 12 subjects per cohort (9 to receive active drug and 3 to receive placebo). Cohort 2 with 13 subjects per cohort (9 to receive active drug and 4 to receive placebo), and Cohort 3 with 14 subjects per cohort (9 to receive active drug and 5 to receive placebo). All doses in Part 2 will be under fed conditions.

For Part 3, 30 subjects are planned to be enrolled. There are 3 groups planned with 10 subjects per group. All subjects will receive active drug under fasted or fed conditions.

Additional cohorts may be enrolled if it is deemed appropriate by the Sponsor to repeat a dose level, to study another dose level, or to increase cohort size (subject numbers).

The number of subjects selected for the study was based on the adequate number considered to provide sufficient safety data. This study has not been formally powered.

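### Protocol version 8.0 adds Cohort 7 but keeps a Part 1 total of 50 to 60; its design now gives at least 69, and the SAP says 60 to 70

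*Protocol*

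**What the plan says.** Protocol Section 6.1 builds the Part 1 number from its components. The SAD element reads, up to its last word, "For 6 dose levels, 6 cohorts of 8 subjects will be used, 6 to receive active drug and 2 to receive placebo, all under fasting". For the food-effect element the text reads, again up to its last word, "The fed group will enroll at least 10 subjects, which will yield complete data for at least 8 subjects if at most 2 fail to". In the fasted arm, data from the 6 active subjects of Cohort 4 "will be combined with data from 3 additional subjects to be enrolled in this fasted group". The section then concludes "Thus, the total number of subjects planned is at least 50 to 60".

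Further down, the same section states "Additional cohort, Cohort 7: Eight (8) subjects will be enrolled, 6 to receive active drug and 2 to receive placebo". The total is not revisited.

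The synopsis (Number of subjects, Part 1) words the total differently: "Plan to enroll 50 to 60 subjects in 6 SAD cohorts". It drops the qualifier of a minimum, gives each cohort 8 subjects, and introduces the food-effect cohort afterwards as an addition. For the fasted arm it says "At least three additional subjects will be enrolled to be dosed in the fasted group", where Section 6.1 gives a plain 3.

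SAP Section 1 says the plan is based on protocol version 8.0, which already contains Cohort 7. SAP Section 4 counts seven cohorts of 8, adds the same food-effect subjects, and concludes "Thus, the total number of subjects planned is at least 60 to 70".

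**The concern.** The planned number of subjects is a basic design statement, and here the components do not add up to it. Cohort 7 is firm: Section 6.1 and the synopsis say its subjects will be enrolled, it is listed as Dose Level 7, and it has its own row in Table 6 (6 active, 2 placebo). The clause under which further cohorts may be enrolled is separate. The Summary of Changes shows that version 8.0 raised the Part 2 number from 36 to 39 in both the synopsis and Section 6.1, while the Part 1 number stayed as it was.

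Two documents tied to the same protocol version therefore give different Part 1 totals. Anyone setting actual enrolment beside the plan would find 8 or 9 subjects more than the protocol's upper figure, yet agreement with the SAP. What is at stake is the consistency of the record, not inference.

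**Working it through.** No power formula applies, because Section 6.1 says the study was not formally powered. The check is a head count.

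| Input | Value | Source |
|---|---|---|
| SAD cohorts in the protocol's sum | 6 cohorts of 8 | Protocol 6.1 |
| New fed subjects | at least 10 | Protocol 6.1, synopsis |
| New fasted subjects | 3 (6.1); at least 3 (synopsis, Section 3) | as shown |
| Cohort 4 subjects reused in the fasted arm | 6, already counted in the SAD cohorts | Protocol 6.1 |
| Cohort 7 | 8 | Protocol 6.1, Table 6 |
| Dosed in Cohorts 1 to 6 | 47 (Cohort 4 enrolled 7) | Protocol 1.6 |
| SAD cohorts in the SAP's sum | 7 cohorts of 8 | SAP 4 |

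**1. The protocol's own figure.**
- SAD cohorts: 6 × 8 = 48.
- New food-effect subjects: 10 + 3 = 13.
- Sum: 48 + 13 = 61.
- With actual enrolment in Cohorts 1 to 6: 47 + 13 = 60.

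The upper figure of 60 is reproduced to within one subject from the plan, and exactly from actual enrolment. The lower figure of 50 is not derived anywhere.

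**2. Adding Cohort 7.**
- Planned: 61 + 8 = 69. Excess over 60: 69 − 60 = 9, and 9/60 = 15%.
- With actual enrolment: 60 + 8 = 68. Excess over 60: 68 − 60 = 8, and 8/60 = 13%.

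Both counts are minimums, because the food-effect groups are set as minimums.

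**3. The SAP's figure.**
- 7 × 8 = 56, and 56 + 13 = 69.
- This lies inside 60 to 70, as does 68.

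**4. The synopsis sentence.**
- Six cohorts of 8 hold 48, which is below the bottom of the 50 to 60 assigned to them.

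The protocol and SAP thus agree on every component: 8 per SAD cohort, at least 10 new fed subjects, 3 new fasted subjects, and 8 in Cohort 7. They differ only in whether Cohort 7 is inside the total.

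**The case against.** The best defence is that the protocol's total was never meant to include Cohort 7. The protocol calls it an additional cohort throughout, the text before Table 6 separates it from the six planned ones, and its 8 subjects are stated openly in both the synopsis and Section 6.1. On the six-cohort basis the sum is right to within one subject. Much of this stands: the sum was sound for six cohorts, and the protocol-SAP difference is one of counting basis. It does not rescue the total as it now reads, because neither Section 6.1 nor the synopsis says that Cohort 7 is excluded. It also does not explain the synopsis sentence that puts 50 to 60 subjects into cohorts holding 48.

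A reader might infer more than the documents support:

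- *That the design overshoots an approved maximum by 15% to 38%.* Section 6.1 says at least, so its range is a floor. The 38% compares 69 with the bottom of that floor: (69 − 50)/50. The synopsis does omit the qualifier, but nothing there makes 60 a cap.
- *That the design exceeds the range even without Cohort 7.* That rests on 61 against 60, and disappears with the 47 subjects actually dosed.
- *That subjects escaped ethics review.* Cohort 7's numbers are explicit. Section 3 requires the review board to be notified of additional cohorts, and Section 3.1 has the next cohort wait for its approval.
- *That an analysis is affected.* SAP 6.4 summarises disposition for enrolled subjects, and SAP 6.9 summarises extent of exposure for Part 2 only. Neither uses a planned Part 1 denominator.
- *That the synopsis plans 71 to 81 subjects* (50 to 60, plus 13, plus 8). Section 6.1 gives the same 50 to 60 with the food-effect subjects already included, so a misattributed total is the more plausible reading.

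**Conclusion.** The point stands as an outdated total. Protocol version 8.0 added Cohort 7 without updating the Part 1 number, so the upper figure of 60 falls 9 subjects short of the planned minimum of 69, or 8 short of the 68 obtained from actual enrolment. Essentially all of that gap is Cohort 7. The protocol total consequently conflicts with SAP Section 4, and the synopsis separately attributes the range to the wrong set of cohorts. The SAP's range is not an arithmetic error, since it contains 69.

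The result assumes that Cohort 7 belongs in the Part 1 total, that the food-effect groups enrol their stated minimums, that the 6 reused Cohort 4 subjects are counted once, and that no one is replaced. Larger food-effect groups or replacements, which Section 8.4 permits, would raise the count. No power, error rate, estimate or dosing decision changes.

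**What to change.** - **Protocol Section 6.1:** restate the Part 1 total as at least 69, with the sum shown: 7 × 8 SAD subjects, at least 10 new fed, and at least 3 additional fasted. Keep it as a minimum. A flat 69 would turn minimums into an exact count, and Cohort 4 enrolled 7.
- **Synopsis, Number of subjects, Part 1:** give the same minimum, and attribute it to the SAD cohorts including Cohort 7 plus the food-effect cohort, not to the 6 SAD cohorts alone.
- **SAP Section 4:** replace the range with the same minimum, so that both documents carry one number.

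The Part 2 (39) and Part 3 (30) figures already agree between the documents and need no change. The cost is wording in three places, with no extra subjects, procedures or analyses.

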6.2 Blinding (Parts 1 and 2)

All subjects and clinical staff (except for the unblinded pharmacy staff) will be blinded to treatment. An unblinded pharmacy staff will be required at the Clinical Site to comply with the study's randomization and blinding requirements. At the Clinical Site, prior to study initiation, the Principal Investigator will be responsible for designating a qualified pharmacy staff to serve as the unblinded pharmacy staff in the study. Unblinded pharmacy staff may dose subjects but may not participate in any subject assessments.

Throughout the study, the designated unblinded pharmacy staff will be responsible for all drug accountability issues, including preparing, labeling, dispensing, and dosing study drug according to the randomization code provided, yet remain independent of all

subject assessments. The pharmacy staff will follow the Standard Operating Procedures (SOPs) and Work Instructions related to pharmacy services and protocol-specific requirements.

Randomization codes will be provided to the unblinded pharmacy staff. Confirmation of receipt of the randomization code will be required by the Sponsor. The unblinded pharmacy staff will be responsible for maintaining the blind, consistent with protocol design, throughout the study. All blinded information will be kept in the pharmacy file. Access to the blinded information in the pharmacy file will be restricted.

The subjects, Principal Investigator, and all other study personnel involved with subject assessments will remain blinded to the actual treatment assignments of the subjects. The Principal Investigator will be ultimately responsible for ensuring that the integrity of the blind is maintained throughout the study at the site and will be required to notify the Sponsor in the event of any breaking of the blind for any reason.

Part 3 is open-label.

